The exposure time will be measured using patient-exposure-week (PEW). PEW of TI periods over the first 28-weeks will be added up to a cumulative number of weeks. For a patient with at least one TI response period over the first 28-weeks, the last TI response period will end with the date of a subsequent RBC transfusion, visit date at week 28, date of the end of study or treatment discontinuation due to AE/SAE or death, whichever comes earlier. For a patient with no TI response period over the first 28 weeks, the cumulative number of PEW will be set to zero.

The cumulative number of PEW over the first 28 weeks of treatment period will be summarized using descriptive statistics by treatment group. Treatment comparison will be based on a non-parametric ANCOVA (stratified rank ANCOVA) described in Stokes, Davis, and Koch 2000. The analysis will use baseline hemoglobin as covariate, treatment arm as fixed effects, controlling for stratification factors (baseline endogenous EPO level, IPSS-R risk category and RBC transfusion burden). See [Section 5.5](#) for the definition of number of pRBC (packs of red blood cells) transfusions at baseline.

Since it is expected that the sample sizes are not large for all strata, the following steps and SAS codes are to be used:

Step 1: Compute the ranks of the response variable and covariate across the two treatment groups.

Sample SAS code:

```
PROC RANK TIES = mean OUT = ranks;  
  BY <strata_var>;  
  VAR <baseline_var> <response_var>;  
RUN;
```

Step 2: With the ranks of response variable, an ANCOVA model will be fitted including the baseline ranks and stratification factor as covariates.

Sample SAS code:

```
PROC MIXED DATA = ranks;
  CLASS <strata_var>;
  MODEL <R_response_var> = <R_Baseline_var> <strata_var>/OUTP = res;
RUN;
```

Step 3: CMH mean score statistics will be used to compare the two treatment groups using the values of the residuals obtained from step 2 as scores. The p-value obtained will be reported.

Sample SAS code:

```
PROC FREQ DATA = res;
  TABLES <strata_var>* <treatment_var>*resid/CMH2;
RUN;
```

The p-value from the stratified CMH chi-square will be provided for the test of the null hypothesis that there is no difference in two treatment groups.

Week 28 and week 52 are the analysis endpoint for 28-week and 52-week analysis respectively.

This analysis will take into account the potential intercurrent events as follows:

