1. Treatment discontinuation (such as: due to Disease progression, Liver function, Patient decision, Investigator decision, AE/SAE, etc.): using While on treatment strategy: PEW of TI will be estimated in the duration beginning with the first dose date (Day 1) and ending with the date of end of treatment or last visit date at week 28/52, whichever comes earlier.
2. Death: using While on treatment strategy: Treatment effect while on-treatments of interest. PEW of TI will be based on RBC transfusion records up to the date of end of treatment or last visit date at week 28/52 or death, whichever comes earlier.

In addition, the cumulative number of Patient-Exposure-Weeks of TI at week 28 and week 52 will be also summarized using the box-whisker plot by treatment groups.

12.3.3.4. Number of pRBC Transfused compared to Baseline over the first 28 Weeks of the Treatment Period

Descriptive statistics of the number (pRBC/8 weeks) of pRBC transfused and number (pRBC/8 weeks) of pRBC transfused change from baseline will be presented by treatment group using FAS and PPS. See [Section 5.5](#) for the definition of number of pRBC transfusions at baseline.

Treatment comparison will be performed for the number (pRBC/8 weeks) of pRBC transfused change from baseline based on a non-parametric ANCOVA (stratified rank ANCOVA) using baseline hemoglobin and baseline pRBC transfusions (pRBC/8 weeks) as covariate, treatment arm as fixed effects, controlling for stratification factors baseline endogenous EPO level and IPSS-R risk category. The p-value obtained will be reported for the test of the null hypothesis that there is no difference in two treatment groups.

Week 28 and week 52 are the analysis endpoint for 28-week and 52-week analysis respectively.

Similar methods will be used as in [Section 12.3.3.3](#). Similar Strategies will be implemented for potential intercurrent events.

12.3.3.5. Proportion of Patients Who Achieved TI for ≥ 20 consecutive Weeks (140 consecutive Days) anytime during the study

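### The rank ANCOVA for Tests 5 and 6 uses unstandardised within-stratum ranks, which over-weights large strata and loses some efficiency but not validity

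*SAP*

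**What the plan says.** SAP 12.3.3.3 analyses Test 5 by a stratified rank ANCOVA with baseline hemoglobin as covariate, "controlling for stratification factors (baseline endogenous EPO level, IPSS-R risk category and RBC transfusion burden"). Three two-level factors give eight strata. The procedure has three steps.

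- Step 1 ranks response and covariate by "PROC RANK TIES = mean OUT = ranks" with "BY <strata_var>".
- Step 2 fits one model to the response ranks, with the covariate ranks and stratum as terms, and keeps the residuals.
- Step 3 compares the arms by the CMH mean score statistic, "using the values of the residuals obtained from step 2 as scores": "TABLES <strata_var>* <treatment_var>*resid/CMH2".

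The code blocks are labelled as samples, but the lead-in is prescriptive: "Since it is expected that the sample sizes are not large for all strata, the following steps and SAS codes are to be used".

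For Test 6 (SAP 12.3.3.4, change in pRBC transfused) the SAP says "Similar methods will be used as in" 12.3.3.3. The stratification factors there are EPO level and IPSS-R only, so there are four strata; baseline transfusions become a covariate. SAP 12.3.4.7 uses the same method for triglycerides, which is exploratory. In SAP Table 4 each test is reached only if the one before it succeeds.

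**The concern.** Raw ranks in a stratum of n patients run from 1 to n. Step 2 removes the stratum means, but no step rescales the spread. A patient in a large stratum therefore carries more weight in the CMH statistic than one in a small stratum. The SAP chose these steps because it expects small strata ("Since it is expected that the sample sizes are not large for all strata"), and unequal stratum sizes are where raw ranks lose most. The weighting is neither stated nor justified.

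What is at stake is power. Test 5 comes before Test 6, 20-week TI (Test 7) and the three patient-reported outcomes (Tests 8 to 10), and its failure ends formal testing of all of them.

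**Working it through.** **Inputs from the documents.** N = 140 in the double-blind component (SAP 17); 3:2 allocation within stratum and a cap of 30% on 1-pRBC patients (SAP 3.3); two-sided 0.05 (SAP 12.1); planning rates of 56% v 13% and 35% v 5% (SAP 3.2); patient-exposure-weeks set to zero for non-responders (SAP 12.3.3.3).

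**Assumptions.** The EPO and IPSS-R splits are not given, so a range is shown. The three factors are taken as independent and the treatment effect as equal in every stratum.

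**The plan's own figure.** The SAP states at least 90% power for the primary endpoint by Fisher's exact test. Recomputed power is 99.9% at 72:48 with 56% v 13%, and 99.9% at 96:64 with 35% v 5%, so the statement holds as a lower bound. The SAP gives no power figure for Tests 5 or 6.

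**Efficiency.** For a common effect, the rank-sum signal in a stratum of n patients is proportional to n², and its null variance to n²(n+1). Dividing ranks by n+1 gives each stratum information roughly proportional to n with equal weight. Raw ranks add an extra weight w = n+1, so

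efficiency = (Σ w·n)² / (Σ n · Σ w²·n).

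**Worked case, Test 5.** Take 30% with 1 pRBC, 25% with EPO above 200 and 25% intermediate risk.

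- Stratum sizes: 55.1, 23.6, 18.4, 18.4, 7.9, 7.9, 6.1, 2.6.
- Σ n = 140; Σ w·n = 4,581; Σ w²·n = 203,352.
- Efficiency = 4,581² / (140 × 203,352) = 0.74. The loss of 0.26 is like losing about 37 of 140 patients.
- The largest stratum holds 55.1/140 = 39% of patients but 55.1 × 56.1/4,581 = 67% of the signal weight.

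**Over other splits (N = 140).**

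| Test | Splits | Information lost |
|---|---|---|
| 5 (8 strata) | 50/50, 50/50, 70/30 | 8% |
| 5 | 60/40, 60/40, 70/30 | 14% |
| 5 | all 70/30 | 23% |
| 5 | all 80/20 | 27 to 29% (30% large-sample) |
| 6 (4 strata) | both 60/40 | 6% |
| 6 | both 70/30 | 17% |
| 6 | both 80/20 | 20% |

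Equal strata lose nothing.

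**Simulation of the three steps, Test 5.** N = 140, 30/25/25% splits, responders' TI weeks assumed to be spread between 8 and 28.

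| Responders | Power, raw | Power, rank/(n+1) |
|---|---|---|
| no difference | 5.0% | 4.8% |
| 56% v 13% | 99.7% | 99.9% |
| 35% v 5% | 97.7% | 99.3% |
| 40% v 18% | 64% | 77% |
| 48% v 30% | 43% | 53% |

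For Test 6, with both factors split 70/30 and a 0.5 SD shift, power is 70.3% raw and 78.7% standardised.

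**The case against.** **The size rests on assumptions.** This stands. The only stratum-size fact in the documents is the 30% cap. A reader might infer that a quarter of the information is lost, or that a quarter is the upper limit. The documents support neither: the Test 5 loss could be 8% or close to 30%, and Test 6 has four strata and a smaller range.

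**The test is valid.** This stands too. A reader might infer an inflated type I error, but ranking, residuals and CMH variance are all handled within stratum, and null rejection is about 5% either way.

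**Little is lost at the planned effects.** Correct: about 98% or more under both SAP scenarios. The losses of 10 to 13 points come from smaller effects that the documents do not name. At 48% v 30% the primary test itself fails in about 44% of simulated trials, so Test 5 is often not reached. The gap remains among trials that do reach it.

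**Sparse strata may be merged.** Protocol 8.3.3.1 drops the most imbalanced stratification factor when strata are too small, for secondary endpoints as well. SAP 12.3.3.3 does not restate that rule. At 30/25/25% splits, dropping one factor leaves efficiency of 0.80 to 0.82, a loss of 18 to 20%. That softens the point without removing it.

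**The change is not free of downside.** Standardised ranks are better when effects are similar across strata. With 45% v 18% responders at EPO up to 200 and no effect above 200, simulated power differs by between zero and 3 points. The SAP treats the influence of EPO on response as an open exploratory question.

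**The code is a sample and cites a textbook.** Whether that source standardises ranks cannot be checked here. The SAP nevertheless directs that these steps and code be used.

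**Conclusion.** The stated code over-weights large strata in Tests 5 and 6. The consequence is lost efficiency, with no bias and no loss of type I error control. If the effect is similar across strata, the loss is about 8 to 30% of the information for Test 5 and about 6 to 20% for Test 6, depending on unstated EPO and IPSS-R splits. It makes almost no difference at the SAP's planning rates. It matters if the effect is materially smaller, because Test 5 guards Tests 6 to 10. This is a cheap improvement to the plan, not the correction of an error that would invalidate a result.

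**What to change.** Before any unblinding, change Step 1 in SAP 12.3.3.3 to within-stratum standardised ranks, rank/(n+1), by adding the NPLUS1 option to PROC RANK for both response and covariate. Leave Steps 2 and 3 as they are. State that 12.3.3.4 uses the same ranks for its response and both covariates, and apply the change to the triglyceride analysis in 12.3.4.7 for consistency. If the sponsor prefers raw ranks, a sentence justifying that weighting would do instead.

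The cost is one code option and a line of text. The one trade-off is that the gain shrinks or disappears if the effect is concentrated in the largest strata.

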12.3.3.6. Mean Change from Baseline in Physical Functioning Subscale of PROMIS

The PROMIS PF item measures self-reported, current capability to carry out activities that require physical actions, ranging from self-care (activities of daily living) to more complex activities that require a combination of skills, often within a social context. The questionnaire will be administered at the Week 1 Day 1, Week 9, Week 17, Week 28 and Week 52 (or EOT). The PF 10-item short form which contains 10 questions will be used in this study, and each item is scored on a 5-point rating scale, with higher scores indicating better functioning. To find the total raw score, sum the values of the response to each question, with the lowest possible raw score is 10; the highest possible raw score is 50.

PROMIS items are not scored as sums, but rather on a standardized T-score metric ([Appendix 19.5](#)) using IRT. The standardized norm-based T-scores will be used in the summary. The mean change from Baseline in the PROMIS-SF v2.0 Physical Function 10b score will be summarized and analyzed. A mixed model for repeated measures (MMRM) with treatment, visit, treatment*visit, and stratification factors as fixed effects, the baseline score value and baseline*visit interaction as covariate will be used to assess treatment difference. The LSM and the corresponding 95% confidence intervals for the differences between roxadustat and the placebo group (roxadustat – placebo) will be presented along with the p-values for the treatment differences resulting from the model. The LSM for the difference will be considered clinically meaningful if it exceeds the distribution-based minimal clinically important difference (MCID) and will be marked in the results, see [Section 19.8.1](#) for details of MCID. An unstructured variance-covariance structure will be used to model the within-patient errors. This variance-covariance matrix will be estimated across treatment groups. If the model fails to converge, then the covariance structure that converges and with the highest REML log likelihood will be used.

Missing values will be handled by the MMRM model, utilizing data from all visits and all patients.

A sensitivity analysis will be conducted using Analysis of Covariance (ANCOVA) model with Last Observation Carries Forward (LOCF) imputation, see [Section 19.8.3](#) for details.

Week 9 and week 52 are the analysis endpoint for 28-week and 52-week analysis respectively, the p-value obtained will be reported.

This analysis will take into account the potential intercurrent events as follows:

1. Treatment discontinuation due to reasons other than AE/SAE: using Treatment-policy strategy: regardless of these intercurrent events occurred;
2. Treatment discontinuation due to AE/SAE: using Hypothetical strategy: A scenario is envisaged in which the patient suffers from the worst quality of life after discontinuation treatment due to AE/SAE. If a patient discontinued treatment due to AE/SAE, all the missing PROMIS-SF v2.0 Physical Function 10b score afterward will be substituted with the worst possible scores before being used in descriptive summary and statistical models.
3. Death: using Treatment-policy strategy: regardless of these intercurrent events occurred. If a patient died, the PROMIS-SF v2.0 Physical Function 10b scores up to death will be used for analysis.

Line plot of mean and mean change from baseline over time with the associated standard error will be provided. A cumulative distribute plot will be presented to show the difference of patients achieving meaningful change in PROMIS-SF v2.0 Physical Function 10b score between two treatment groups.

A by-patient listing will also be provided.

The analysis will be conducted for FAS and PPS.

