Week 35	
 
• Dose adjustment review
 
• Dispense study drug
 
	
 
• CBC (central) and Local Hb
 

Week 39	
 
• Vital signs (BP, HR, RR, and Temp)
 
• Point-of-care urine pregnancy test
 
• Dispense study drug
 
	
 
• Serum chemistries
 
• Serum lipid panel
 
• LFTs
 
• Heparin
 
• Iron biomarkers
 
• Reticulocytes & CHR
 
• CBC (central) and Local Hb
 
• Endogenous serum EPO level
 

Week 43	
 
• Dose adjustment review
 
• Dispense study drug
 
	
 
• CBC (central) and Local Hb
 

Week 47	
 
• Dispense study drug
 
	
 
• CBC (central) and Local Hb
 

Week 52/EOT	
 
• Bone marrow aspirate and biopsy
 
• Physical Exam
 
• Vital signs (BP, HR, RR, and Temp)
 
• ECG
 
• ECOG score
 
• Health-related quality of life HRQoL assessments
 
	
 
• CBC (central) and Local Hb
 
• Serum chemistries
 
• LFTs
 
• Iron biomarkers
 
• Heparin
 
• Endogenous serum EPO level
 
• PT, PTT
 
• Serum lipid panel
 
• B12 and folate
 
• C-reactive protein
 
• Reticulocytes & CHR
 
• Serum pregnancy (for females of childbearing capability)
 

4 Weeks Post-EOT	
 
• Physical Exam
 
• ECOG score
 
• Vital signs (BP, HR, RR, and Temp)
 
• Health-related quality of life (HRQoL)
 
	
 
• CBC (central) and Local Hb
 
• Serum chemistries
 
• LFTs
 
• Iron biomarkers
 

**Table 2 Additional Study Procedures/Assessments and Blood Sampling by Visit for the 52-Week Treatment Period, EOT and Post-EOT (Appendices A, B, K)**

Study Visit	Procedures and Assessments	Blood Samples

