**Appendix B - Patients who Discontinue Study Medication Prior to Week 52**

Procedures	EOT 	Post - EOT 	Every 8 weeks assessment from Post-EOT WK 4 visit. Last visit at Week 52 from first dose.	
		WK 4	WK 12	→
Informed consent signature				
Eligibility Review 				
Med History/ Demographics				
Physical Exam	X	X		
Weight 				
HbsAg, anti-HCV AB, HIV				
Endogenous serum EPO Level 	X	X	X	
B12, Folate	X	X		
PK 				
ECG 	X	X		
Bone marrow aspirate and biopsy 	X			
Vital signs 	X	X	X	
ECOG Score 	X	X		
Serum Lipid Panel	X	X		
LFTs 	X	X	X	
Serum chemistry 	X	X	X	
PT, PTT	X	X		
Hepcidin	X	X	X	
Pregnancy test 	X	X		
C-reactive protein	X	X		
Recording of transfusions 	→			
CBC 	X	X	X	
Local Hemoglobin	X	X	X	
Reticulocyte count; CHr	X	X		
Iron Biomarkers 	X	X	X	
Registration/Randomization to the study				
HRQoL Questionnaires 	X	X		
Study drug dosing				
Study drug dispensation				
Dose adjustment review				
AEs/Con Meds/Procedures	→			

For footnotes please refer to [Appendix A](#)

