12.3.2. Sequential Gatekeeping Procedure

Once the primary hypothesis has been rejected for the primary endpoint, the primary endpoint at week 52 and the secondary endpoints in the order specified in the Table 4 will be tested using a sequential gatekeeping procedure, in order to maintain the overall two-sided type I error of 0.05. If p-value from a test is < 0.05 , the claim of superiority will be considered successful, and the test will progress to the next comparison in sequence as follows.

Table 4: Sequential Gatekeeping Procedure

Test	Variable	Comparison
1	Proportion of patients who achieved TI ≥ 56 consecutive days (e.g., 8 weeks) since first dose in the first 28-weeks of treatment	Superiority of roxadustat versus placebo
2	Proportion of patients who achieved TI ≥ 56 consecutive days (e.g., 8 weeks) since first dose in the 52-weeks of treatment	Superiority of roxadustat versus placebo
3	Proportion of patients who achieved TI ≥ 56 consecutive days (e.g., 8 weeks) anytime during the study	Superiority of roxadustat versus placebo
4	Proportion of patients who achieved $\geq 50\%$ reduction in number of pRBC transfusions over 8 weeks compared to their Baseline for any 8-week period during the study	Superiority of roxadustat versus placebo
5	Cumulative number of patient-exposure-weeks (PEW) of TI over the first 28 weeks of the treatment period	Superiority of roxadustat versus placebo
6	Number of pRBC transfused change from baseline over the first 28 weeks of the treatment period	Superiority of roxadustat versus placebo
7	Proportion of patients who achieved TI for ≥ 20 consecutive weeks (140 consecutive Days)	Superiority of roxadustat versus placebo

8	Mean change from baseline in the PROMIS-SF v2.0 Physical Function 10b score at week 9	Superiority of roxadustat versus placebo
9	Mean change from baseline in the PROMIS-SF v1.0 Fatigue 13a score at week 9	Superiority of roxadustat versus placebo
10	Mean change from baseline in EQ-5D-5L VAS score at week 9	Superiority of roxadustat versus placebo

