19.3. Data Handling Conventions

19.3.1. Analysis Windows

Tables below present the visits assigned for efficacy and safety analyses corresponding to the range of treatment days (window) during which an actual visit may have occurred.

The analysis windows will be only applied to those assessments up to the day before the first week of follow-up visit. Assessments obtained afterwards are considered follow-up assessments. For follow-up assessments, only follow-up assessments on scheduled follow-up visits (i.e. nominal follow-up visits) will be summarized unless otherwise specified.

If more than one assessment is available in the same window, the last assessment is used for analysis. Assessments that do not fall in any windows will not be included in analyses unless otherwise specified. However, all post-baseline assessments will be used for PCS value determination and all assessments will be presented in the data listings.

Table 7.1 Analysis Visit Windows (General)

Analysis Visit	Visit Scheduled Day ^a	Window
Baseline	Day 1	Up to Day 1 Pre-Dose
Week 3	Day 7*(Week # -1)+1	[Day 1 Post-Dose, Scheduled Day +7)
Weeks 5, 7, 9, 11...27	Day 7*(Week # -1)+1	[Scheduled Day -7, Scheduled Day +7)
Week 28 ^b	Day 7*(Week #)+1	[Scheduled Day -7, Scheduled Day +7)
Weeks 31	Day 7*(Week # -1)+1	[Scheduled Day -7, Scheduled Day +14)
Week 35, 39, 43	Day 7*(Week # -1)+1	[Scheduled Day -14, Scheduled Day +14)
Week 47	Day 7*(Week # -1)+1	[Scheduled Day -14, Scheduled Day +21)
Week 52 ^c	Day 7*(Week #)+1	[Scheduled Day -21, Up to Week 4 Follow up)

^a: Relative to the first study medication date. For example, Day 1 = the first dose date of study medication.

^b: Week 28 visit should be conducted at the end of 28 weeks of treatment (2 weeks after Week 27 Visit).

^c: Week 52 Visit should be scheduled at the end of 52 weeks treatment (6 weeks after Week 47 visit).

Table 7.2 Analysis Visit Windows for Lipid Parameters

Derived Visit	Visit Scheduled Day ^a	Window
Baseline	Day 1(first dose day)	Up to Day 1 Pre-Dose
Week 5	Day 7 * (Week # -1) +1	[Day 1 Post-dose, Scheduled Day + 56)
Week 21	Day 7 * (Week # -1) +1	[Scheduled Day - 56, Scheduled Day + 28)
Week 28 ^b	Day 7 * (Week #) +1	[Scheduled Day - 28, Scheduled Day + 35)
Week 39	Day 7 * (Week # -1) +1	[Scheduled Day - 35, Scheduled Day + 49)
Week 52 ^c	Day 7 * (Week #) +1	[Scheduled Day -49, Up to Week 4 follow-up)

^a: Relative to the first study medication date. For example, Day 1 = the first dose date of study medication.

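### The quality-of-life endpoints claim treatment policy for non-AE discontinuation, but apart from the end-of-treatment score no off-drug questionnaire enters the model

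*SAP*

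**What the plan says.** **Strategy.** SAP 12.3.3.6 states, for PROMIS Physical Function: "Treatment discontinuation due to reasons other than AE/SAE: using Treatment-policy strategy: regardless of these intercurrent events occurred". Sections 12.3.3.7 (Fatigue) and 12.3.3.8 (EQ-5D VAS) repeat it, as do the three quality-of-life rows of Table 1 in SAP 4.2.2, all of which refer to Week 9.

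**Timepoints.** Test 8 of the gatekeeping sequence is "Mean change from baseline in the PROMIS-SF v2.0 Physical Function 10b score at week 9". Tests 9 and 10 use the same week. Section 12.3.3.6 adds: "Week 9 and week 52 are the analysis endpoint for 28-week and 52-week analysis respectively".

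**Missing data.** "Missing values will be handled by the MMRM model, utilizing data from all visits and all patients". SAP 19.8.2 adds an LOCF ANCOVA as a sensitivity analysis for the two PROMIS scores only.

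**Windows.** SAP 19.3.1 applies the windows only until the day before the follow-up visit. "Assessments obtained afterwards are considered follow-up assessments", and these are summarised only at their nominal follow-up visit. If one window holds several forms, the last is used.

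**Collection.** The row "HRQoL Questionnaires 15" in Protocol Appendix B is marked at EOT and Post-EOT Week 4 and is blank for the 8-weekly visits. Protocol Table 2 agrees. The SAP's own schedule lists Day 1, Weeks 9, 17 and 28, and Week 52 or EOT. Early stoppers stay in the study to Week 52 (Protocol 4.3, SAP 3.1).

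**The concern.** Under treatment policy, the score that counts is the one at the visit in question, whether or not the patient is still on drug. That requires off-drug scores to be collected and used. Here the one form taken clearly off drug is collected and then left out of every analysis visit, and nothing is collected after it.

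The SAP handles this differently for transfusion independence at any time (12.3.3.1), where transfusions after the end of treatment count. The quality-of-life sections have no equivalent rule.

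What is at stake is the meaning of the reported effect. It would be presented as an effect regardless of discontinuation, when it is partly a while-on-treatment effect (Week 9) and partly an effect assuming continued treatment (later visits). Protocol 2.6 says the erythropoietic effects reverse when treatment stops, so the difference plausibly flatters roxadustat.

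**Working it through.** The plan gives no figure to reproduce on this point. The check is to place an early stopper's forms in the windows.

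**1. Windows in days (SAP Table 7.7).** The scheduled day is 7 × (week − 1) + 1 for Weeks 9 and 17, and 7 × week + 1 for Weeks 28 and 52.

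- Week 9: day 57; window day 1 post-dose to below 57 + 28 = 85, so days 1–84.
- Week 17: day 113; 113 − 28 = 85 to below 113 + 42 = 155, so days 85–154.
- Week 28: day 197; 197 − 42 = 155 to below 197 + 84 = 281, so days 155–280.
- Week 52: day 365; from 365 − 84 = 281 up to the Week 4 follow-up.

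The windows meet without gaps.

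**2. Where the forms fall.** The last dose precedes the EOT assessments (Protocol Appendix A, footnote 17), and the Post-EOT visit is at least 28 days after dose/EOT (footnote 19). The interval from last dose to EOT is not stated; I assume 2 days. The Post-EOT form is placed at its earliest day, last dose + 28.

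| Last dose (day) | EOT form, and the visit it fills | Post-EOT form, from day | Window containing that day | Used? |
|---|---|---|---|---|
| 15 | 17, Week 9 | 43 | Week 9 | No |
| 40 | 42, Week 9 | 68 | Week 9 | No |
| 70 | 72, Week 9 (displaces the day-57 score) | 98 | Week 17 | No |
| 100 | 102, Week 17 | 128 | Week 17 | No |
| 150 | 152, Week 17 | 178 | Week 28 | No |
| 300 | 302, Week 52 | 328 | Week 52 | No |

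One form after stopping therefore enters whenever EOT is completed. The Post-EOT form never does, although by day it can fall within Week 9 for any last dose up to 84 − 28 = day 56.

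**3. What the model estimates.**

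- *Week 9:* a patient who stops early and completes EOT is observed, but with a score taken around the last dose. That is close to while-on-treatment. Missing at random matters at Week 9 only if EOT was not completed.
- *Visits after the window holding EOT:* no value exists. The MMRM predicts from the patient's earlier scores and the pattern among patients still contributing data, so it estimates an effect close to continued treatment. At Week 52 this covers those who stop before about day 281.

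**4. Illustration at Week 52; every input is an assumption.** Let δ be the on-drug benefit, d the proportion stopping for non-AE reasons and f the share of benefit lost. If stopping is unrelated to outcome, the treatment-policy effect is δ(1 − d·f), while the missing-at-random estimate stays near δ. With δ = 4:

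- d = 0.10, f = 0.5: 4 × 0.95 = 3.8
- d = 0.40, f = 1: 4 × 0.60 = 2.4

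A large-sample simulation (SD 8, correlation 0.6, regression on the last on-drug score) gave treatment-policy values of 3.85 and 2.41 for these two cases, against 4.05 and 4.04 under missing at random.

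**The case against.** The strongest reply is that the EOT form is itself taken after the last dose and is windowed by study day. A reader might infer that no questionnaire taken after stopping can enter, and that Tests 8 to 10 therefore estimate an effect as if stoppers had stayed on drug. The documents do not support that. At Week 9 the EOT score stands in for the early stopper, and the prediction problem lies mainly at Weeks 28 and 52, outside the gatekeeping sequence. This part of the reply stands.

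Four further points:

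- **Size.** Protocol 4.3 lists lack of efficacy among the reasons for stopping. Such patients may have little benefit to lose, and the MMRM also conditions on their own EOT score. Both would shrink the gap. This stands.
- **Version.** The protocol supplied is Amendment 02, whereas the SAP follows Amendment 03. The blank 8-weekly column cannot be asserted for the governing version. This also stands, but the window rule and the Week 9, 17, 28 and 52 (or EOT) schedule are in the SAP itself.
- **Sensitivity analysis.** The LOCF ANCOVA does not rely on the MMRM's missing-data assumption. However, it carries the EOT score forward, adds no later off-drug data and does not cover EQ-5D VAS. It does not answer the point.
- **EQ-5D wording.** SAP 12.3.3.8 describes the analysis as including patients with a value at the specific visit, which gives early stoppers no further weight at later visits.

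**Conclusion.** The mismatch between label and data is real for all three endpoints. At Week 9 the analysis is roughly while-on-treatment for early stoppers, even when a later off-drug form lies within days 1–84. After the window holding EOT it is hypothetical, resting on missing at random. Neither is treatment policy.

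The direction is plausibly favourable to roxadustat, provided that quality of life follows the reversible erythropoietic effect. The size cannot be determined: the documents give no non-AE discontinuation rate and no rate of loss after stopping. A reader might turn this into an overstatement of 1/(1 − d) − 1, for example 11% at d = 10% or 43% at d = 30%. That requires an assumed dropout rate, full average benefit in every stopper and total loss of it. It does not apply at Week 9 to patients with an EOT form.

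This is a clear inconsistency in secondary endpoints and worth correcting. It does not touch the primary analysis.

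**What to change.** 1. In SAP 19.3.1 and Table 7.7, for patients who stop early for non-AE reasons, assign HRQoL forms to visits by study day regardless of treatment status, so that Post-EOT Week 4 forms enter the MMRM.
2. For these forms, use the one closest to the scheduled day when a window holds more than one, in place of the last. With the timings above, a last dose on day 40 then gives Week 9 the day-68 form (11 days from day 57) instead of the day-42 form (15 days). A last dose on day 70 keeps the day-57 score at Week 9, and the day-98 form fills Week 17.
3. Keep the Week 56 form of patients who complete 52 weeks out of the Week 52 window.
4. Off-drug data will still be absent for many stoppers: at Week 28 for last doses before about 155 − 28 = day 127, and at Week 52 before about 281 − 28 = day 253. Describe those estimates in 12.3.3.6 to 12.3.3.8 as hypothetical, under missing at random. Table 1 has quality-of-life rows for Week 9 only, so it needs no entry for later weeks.
5. Check the HRQoL schedule against Amendment 03.

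The cost is SAP wording and slightly more programming, and the estimate may become slightly less favourable. Adding questionnaires to the 8-weekly visits would close the remaining gap. However, it needs a protocol amendment, and SAP Section 17 reports 140 patients already enrolled, so visits already past could not be recovered. It is not needed to bring the label and the analysis into line.
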